6.4 Administration Rate

Prior clinical trials have used rates up to 30×10^6 hMSC/min where no infusion related toxicity was observed.

In the proposed study, the cell dose to be delivered is 20 million (20×10^6) and 100 million (100×10^6) hMSC/infusion, reconstituted as 0.25 to 1.25 million hMSC/ml, in the following total volume:

80 ml for the 20 million dose (0.5 million hMSC/min)

80 ml for the 100 million dose (2.5 million hMSC/min)

Cells are placed in an 80ml bag and will be delivered at a rate of 2ml/min, and delivered at a maximum rate of 2.5×10^6 hMSC/minute and will last approximately 40 minutes for both doses

The infusion bag will be flushed with an additional 25 ml of 0.9% normal saline at the completion of allo-hMSC infusion and delivered at a rate of 2ml/min.

6.4.1 Infusion Monitoring

Subjects will be monitored in the Clinical Translational Research Site (CTRS) at the University of Miami Hospital (UMH) for two hours prior to infusion to establish baseline vital signs (oxygen saturation, heart rate, blood pressure, and temperature) every 15 minutes. Monitoring will also continue throughout the infusion.

Once the infusion is begun, 2L/min oxygen via nasal cannula will be provided if the oxygen saturation drops below 90% on room air. The infusion will be stopped if the oxygen saturation does not return to >93% within 3 minutes of initiating supplemental oxygen or if the subject requires greater than 2L/min supplemental oxygen to achieve the required saturation of >93%. If a subject requires the addition of oxygen, it will be continued for 4 hours after the completion of the infusion. At that time, oxygen will be weaned off to maintain a saturation >93% on room air.

6.5 Concomitant Therapy

6.5.1 Permitted therapy

Concomitant medications will be recorded on the case report form (CRF), which includes all FDA-approved medications and therapies.

6.5.2 Excluded therapy

Medications and therapies not approved by the FDA are prohibited for the duration of this trial, including participation with any investigational drug or device.

6.5.3 Subject monitoring

All aspects of the study will be conducted in accordance with Good Clinical Practice (GCP) as described in the ICH Guideline (CFR ICH Selected Regulations and Guidance for Drug Studies, CFR Title 21 Food and Drugs) all applicable national and local regulations. Monitoring will be conducted by a qualified outside source at the study site.

Monitoring of key safety endpoints will be conducted. If rates significantly exceed the pre-set threshold, then the DSMB will be advised.

6.6 Blinding and Unblinding

To ensure the primary objective of safety with infusing Allogeneic MSCs in diabetic subjects with endothelial dysfunction, the pilot phase of this trial will not be blinded.

In the Randomized Phase, subjects will be randomized into active groups and study personnel will be blinded to treatment assignments. The designated cell-processing technicians will prepare the allogeneic hMSCs for infusion. The investigational agent infusions will be prepared in identical infusion bags and labeled with the identical investigational drug labels as to preserve the blind. The designated technicians in the ISCI Cell Processing Laboratory (CPL) or designee will be responsible for maintaining the investigational product records including randomized treatment assignments by subject identification. Although the subjects and investigator will remain blinded to treatment allocation throughout the study, the blinding is necessary only for the first 28 days of the study, as these timepoints are what are necessary for the short-term efficacy and safety outcomes of the study. The follow up time points at 3 months, 6 months, and 12 months, are for long-term safety and long-term efficacy but do not require blinding. The 28 day data will be used to determine the dose and time point at which MSCs exert the greatest effect on FMD and EPC-CFUs, as designed in the study, in order to design the next study protocol. The 28 day data will be analyzed by the UM Biostatistics group to determine which dose and at which time point within the 28 day follow up period shows the greatest efficacy. These results will be submitted to the NIH DSMB and the FDA.

If, for important medical reasons, unblinding is thought to be necessary, the Investigator may identify the treatment assignment by obtaining the randomization assignment by contacting the Director of Experimental and Clinical Cell Based Therapies at ISCI who is responsible for maintaining randomization records for all subjects.

6.7 Study Investigational Therapy Management

6.7.1 Investigational Product Labeling and Storage

The product label contains the elements required by the CFR and other national and local authorities for investigational products. ISCI CMP will directly store and deliver the designated cell processing technologist in the CPL, and will be kept cryopreserved in liquid nitrogen vapor phase until shortly before administration must be stored in a securely locked enclosure. Access is strictly limited to unblinded CPL personnel prior to preparation for infusion. After preparation for infusion, the Investigator and his or her designees are permitted to administer the Investigational Product only to subjects participating in this protocol.

6.7.2 Investigational Product Accountability Procedures

In accordance with all applicable regulatory requirements, the Cell Processing Laboratory will maintain a record of the investigational products hMSCs received, dispensed, administered, destroyed, or returned. The final disposition of all unused, empty, and partially used Cryocyte™ bags will be handled in accordance with the drug preparation manual.

Liver Function Tests: Albumin, alkaline phosphatase, alanine transaminase (ALT), aspartate aminotransferase (AST), and bilirubin (fractionate if total >1.5 times normal).

Renal Function Tests: creatinine, blood urea nitrogen (BUN), glomerular filtration rate, sodium, potassium, chloride, calcium, total protein, carbon dioxide and glucose.

4 - **Coagulation Tests:** prothrombin time (PT/INR), activated partial thromboplastin time (aPTT) at screening.

5 – Viral Serology testing at screening will include the following: HIV 1 and HIV 2 antibody screen, Hepatitis B (Hep B surface antigen, surface antibody, and core antibody), Hepatitis C antibody, Syphilis (VDRL or RPR, with reflex FTA-antibody if positive), and CMV antibody.

6 – For females of childbearing potential: serum pregnancy test (β HCG) will be completed at screening and within 36 hours before infusion.

7 – During immune monitoring for graft rejection, **Panel reactive antibodies (PRA)** will be performed from the serum of the subjects to check for donor specific antibodies **at Baseline and Month 3 only.**

8 – The following markers may be used for analysis to assess for activated T-cells based upon a CD3 $^+$ CD25 $^+$ (late/chronic T cell activation) or CD3 $^+$ CD69 $^+$ phenotype (early T cell activation).

9 – The following biomarkers may be analyzed at any or all of the time points in Table 1:

Circulating pro-inflammatory markers: serum high sensitivity C-reactive protein (hs-CRP), IL-6, IL-1, and TNF α

Circulating angiogenic factors known to mobilize and recruit EPCs: VEGF, SDF-1 α , and SCF

Transcriptomic/Proteome: DNA (at baseline only), RNA (**at Baseline and Month 3 only**)

10 – Endothelial Progenitor Cell-Colony Forming Units (EPC-CFUs): Blood will be collected in Lavender top tubes (EDTA) for EPC-CFU analysis.

11 - Postdoctoral (experimental laboratory) studies:

The separate blood samples for the immune markers, biomarkers, and EPC-CFUs described above in 7-9 will be obtained 1) to provide storage of critical biomaterials derived from subjects enrolled in ACESO 2) to provide long-term integrity of these biospecimens and samples, and 3) to provide management of samples for postdoctoral studies of immunologic, immunohistochemical, cellular, and molecular analyses of collected samples; including cell-surface markers (CXCR4, C-Kit, & Connexin 43), transcriptomic/proteonomic (DNA, RNA, miRNA, protein samples, and telomerase), growth factors (noted in 8, above), functional Assays (cell growth rate, CFU assay noted in 9 above), CD3, CD25, CD69 (noted in 7 above), and inflammatory (noted in 8 above), but not limited to these. These biospecimens will be used for research purposes only, will be stored without personal identifying information, and will be shared with approved researchers who will conduct studies to improve the understanding of the effects of cell therapies and/or of diabetes disease on cardiovascular function and outcomes.

12- Since trial participants may not be able to come to the investigational site for protocol specified visits during the “Coronavirus Disease 2019” (COVID-19) pandemic, alternative methods for assessments (e.g., phone contact, virtual visit, alternative location for assessment, including local labs or imaging centers) could be implemented when necessary and feasible, and would be sufficient to assure the safety of trial participants. Assessments could be completed as follows:

- Physical Examination could be done via telemedicine using a virtual platform.
- Vital Signs and 12-Lead EKG: If subject has completed an EKG or vital signs within the window specified per protocol with their PCP or any other treating physician a copy could be requested. Alternatively, subjects may record and report their own vital signs or EKG using home testing equipment (such as thermometer, automated blood pressure monitor, pulse oximeter, wearable health devices, or other method for recording vital signs).
- Questionnaires, concomitant medications, and review of adverse events may be completed by study team via email, phone contact, virtual visit or alternative methods.
- Laboratory assessments: A copy of SOC labs (urinalysis, hematology, chemistry, and HbA1c) may be obtained from PCP or treating physician if done within the protocol specified time window. If participant has not completed any laboratory assessments, they may complete this in any local laboratory facility.
- Brachial Artery Ultrasound, Immune Monitoring, EPC-CFUs and Biomarkers Assessment: If participant is willing to come to site to complete this assessment all necessary safety precautions must be taken. Study team will provide the subject with a mask and gloves upon arrival to the site. If subject prefers to complete this assessment at another time, the study team must document that the assessment will be completed out of the protocol specified window and report to the regulatory authorities accordingly.

8 Study Phases and Visits

8.1 Screening Visit

See Table 1 for the procedures and assessment to be performed during the screening visit of the study, which can take place over several days. All screening visit test and procedures will occur upon signing the informed consent form (ICF). No screening exams will take place until the subject is fully informed of the research and signs the consent form.

All subjects will be enrolled at the University of Miami (UM) hospital and clinics. At the time of enrollment, we will review the medical records to ensure that the ADA guidelines for diabetic care are being followed. We will inform the subjects' primary care physician that the subject is enrolled in our study and must continue to follow the ADA guidelines throughout the trial. All the investigators follow these guidelines, and monitoring of the subjects' care by the clinical investigator or principal investigator will be ongoing through the trial at each follow visit.

Physical exam

A complete physical examination will include general appearance, skin, head and neck, Lymph nodes, musculoskeletal/extremities, cardiovascular, chest/lungs, abdomen, and neurological assessment. At screening, information about the physical examination and any significant findings must be recorded in the source documentation at the study site.

Vital signs

Vital sign measurements will be performed at least once on each study visit up to time of discharge. These measurements will consist of height (screening only), weight, respiratory rate, heart rate, blood pressure, oxygen saturation, and temperature. Respiratory rate, heart rate, and blood pressure should be measured in a seated position.

Endothelial function

- Brachial ultrasound testing and blood collection will be performed to assess endothelial function in the diabetic population at screening, baseline and 3 days, 7, 14, 28 days, 3 months, 6 months, and 12 months post stem cell infusion. This will help provide cumulative data in assessing whether or not stem cell infusion improves endothelial function. This test will be done in the morning prior to 12p.m.
- Flow Mediated Diameter percent change (FMD%): All measurements of the brachial artery diameter and FMD will be performed in the morning, in a quiet and dark room and at controlled ambient temperatures between 20°C and 26°C. Studies will be conducted after an overnight fast of at least 10 hours (water is permitted), with the subject's supine and after 10 minutes of rest. The subject's right arm will be comfortably immobilized in an extending position, allowing for ultrasound scanning of the brachial artery 5–10 cm above the

antecubital fossa. In each examination, recording of vessel images will be followed by inflation of a cuff to supra-systolic pressure (40 to 50 mmHg above systolic pressure) for 5 minutes. Then the cuff will be deflated and the brachial artery diameter will be imaged and recorded for 3 minutes. FMD% more than 10% is considered a normal response. Lower than 7% FMD% reflects endothelial dysfunction, which means a high likelihood to develop cardiovascular event in the future. Subjects with negative FMD% results (the artery is constricted after stress and not dilated as was expected) have the worst prognosis.

8.2 Baseline Visit

See Table 1 for the procedures and assessment to be performed during the baseline visit of the study. This visit will occur after all screening tests are completed and it has been determined that the subject meets eligibility criteria. This visit should occur within 2 weeks prior to Day 0 (the infusion visit).

The following endothelial function tests will be performed:

- Brachial ultrasound testing and blood collection will be performed to assess endothelial function in the diabetic population at screening, baseline and 3 days, 7, 14, 28 days, 3 months, 6 months, and 12 months post stem cell infusion. This will help provide cumulative data in assessing whether or not stem cell infusion improves endothelial function.
- Flow Mediated Diameter percent change (FMD%): All measurements of the brachial artery diameter and FMD will be performed in the morning, in a quiet and dark room and at controlled ambient temperatures between 20°C and 26°C. Studies will be conducted after an overnight fast of at least 10 hours (water is permitted), with the subject's supine and after 10 minutes of rest. The subject's right arm will be comfortably immobilized in an extending position, allowing for ultrasound scanning of the brachial artery 5–10 cm above the antecubital fossa. In each examination, recording of vessel images will be followed by inflation of a cuff to supra-systolic pressure (40 to 50 mmHg above systolic pressure) for 5 minutes. Then the cuff will be deflated and the brachial artery diameter will be imaged and recorded for 3 minutes. FMD% more than 10% is considered a normal response. Lower than 7% FMD% reflects endothelial dysfunction, which means a high likelihood to develop cardiovascular event in the future. Subjects with negative FMD% results (the artery is constricted after stress and not dilated as was expected) have the worst prognosis.
- Blood drawn from fasting subjects for biomarker and PRA analysis will be separated and the serum will be frozen until processed as one batch towards the end of the study.

- **Biomarker analysis:** Soluble pro inflammatory cytokines (interleukin 1, interleukin-6, tumor necrosis factor alpha, high-sensitivity C Reactive Protein, and circulating angiogenic factors) (VEGF, SDF-1 α , and SCF) using immunological and ELISA methods.
- **Assay of colony forming units:** Fresh blood will be processed for cell culture assays for endothelial progenitor stem cells colonies counting (a 5 days' protocol). Fifty milliliter of blood will be processed; peripheral-blood mononuclear cells will be isolated by Ficoll density-gradient centrifugation, will be washed twice in phosphate buffered saline with 5% fetal bovine serum and re-suspended in media (EndoCult basal media with supplements; StemCell Technologies, Vancouver, British Columbia, Canada) for EPC colony-forming assay. Cells will be planted on human fibronectin-coated plates (BIOCOAT; Becton Dickenson Labware, Bedford, Massachusetts) at a density of 5X10⁶ cells/well and incubated at 37°C in humidified 5% CO₂. After 48 hours, the non-adherent cells will be re-plated onto fibronectin-coated 24 well plates at a density of 1X10⁶ cells/well. After 5 days, colony forming units (defined as a central core of rounded cells surrounded by elongated and spindle-shaped cells) will be counted manually in 8 wells out of a 24-well plate.

8.3 Day 0 Visit

See Table 1 for the procedures and assessment to be performed during the Day 0 visit of the study. The Day 0 visit will occur after all baseline tests are completed and it has been determined that the subject remains eligible. Once the subject is deemed eligible to continue in the study, the subject will be administered the investigational product.

8.4 Day 3, Day 7, Day 14, and Day 28 (Post-Intervention Visit)

See Table 1 for the procedures and assessment to be performed for Day 3 through Day 28 visit. Outpatient visits should be completed as close to the scheduled visit dates as possible. There will be a window of + 2 days for Day 3 visit, and \pm 2 days for Day 7, Day 14, and Day 28 study visits.

8.5 Month 3, Month 6, and Month 12 (Post-Intervention Visit)

See Table 1 for the procedures and assessment to be performed for the Month 3, Month 6, and Month 12 study visits. Outpatient visits should be completed as close to the scheduled visit dates as possible. There will be a window of \pm 2 weeks for the Month 3 and Month 6 visits. Month 12 will have a window of \pm 6 weeks.

8.6 Genetic Testing

A separate blood sample of about 10mL for gene expression (DNA) profiling of WBC (at baseline visit) and for RNA expression analysis (at baseline and month 3 visits) will be obtained from the study participants, as detailed on Table 1. A separate genetic consent form is completed by the study participants.

All samples will be identified so that they can be linked to individual subjects. These samples may be stored indefinitely. Individual results will not be returned to the subject

or the study physician. The samples will be linked to subjects, but there will be no recontact.

Data presented in publications will not contain individual subjects' clinical characteristics or outcomes; only aggregate data from the entire study will be disclosed.

8.7 Immune Monitoring for Graft Rejection

The studies planned in this protocol will utilize allogeneic mesenchymal stem cells (MSC) in subjects with endothelial dysfunction. The use of an allogeneic graft raises the potential of graft rejection through immune cells resulting in failure of the therapy. MSCs are ideal candidates for allogeneic transplantation because they show minimal MHC class II and ICAM expression and lack B-7 co-stimulatory molecules necessary for T-cell mediated immune responses^{57, 58}. Indeed MSCs do not stimulate a proliferative response from alloreactive T-cells even when the MSCs have differentiated into other lineages or are exposed to proinflammatory cytokines. Previous studies have demonstrated that MSCs have significant immunomodulatory effects, inhibiting T-cell proliferation and prolonging skin allograft survival. Recently human MSCs were shown to alter the cytokine secretion profile of dendritic cells, T cells, and natural killer cells in vitro, inhibiting secretion of proinflammatory cytokines (e.g. TNF- α , IFN- γ) and increasing expression of suppressive cytokines (e.g. IL-10), possibly via a prostaglandin E2 mediated pathway.

In vivo studies of the fate of MSCs have shown that, when transplanted into fetal sheep, human MSCs engraft, undergo site-specific differentiation into various cell types, including myocytes and cardiomyocytes and persist in multiple tissues for as long as 13 months after transplantation in non-immunosuppressed immunocompetent hosts. Further, in vivo studies using rodents, dogs, goats, and baboons demonstrate that allogeneic MSCs can be engrafted into these species without stimulating systemic alloantibody production or eliciting a proliferative response from recipient lymphocytes. These findings, coupled with our demonstration of efficacy of these cells for cardiac repair, solidify the notion of using MSCs as an allograft for successful tissue regeneration.

As part of this protocol we will obtain peripheral blood samples from all subjects to evaluate the presence and/or development of Panel Reactive Antibodies (PRA) and the presence of activated T cells. Heparinized (green top) and Serum Separator Tube (SST) (which are either gold top or red tiger vacutainer tubes), approx. 15 cc total blood, will be collected at different time points during the study (please reference Table 1). Peripheral blood mononuclear cells (PBMC) will be isolated from heparinized blood by Eicoll sedimentation and will be viably cryopreserved for planned assessments of T cell activation.

Two of the best-accepted markers of T cell activation are CD69 and CD25 (IL-2 receptor α). We will monitor the activation of T cells by flow cytometric analysis of CD3+CD25+CD69+ cells in thawed PBMC. CD69 is an immediate/early marker of CD3+ T cell activation while CD25 expression increases within 1-2 days of activation and remains sustained over the intermediate-long term during chronic immune activation. Given the differences in the kinetics of CD69 and CD25 up regulation, assessment of

both activation phenotypes (CD3+CD69+ and CD3+CD25+) will maximize the sensitivity of detection of T cell activation following allogeneic hMSC infusion.

Additionally, in female subjects who receive allogeneic hMSCs, the stored baseline serum will be analyzed to evaluate the antibody responses to HLA and H-Y antigens.

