5. DONORS

5.1 Normal Donor Eligibility

Donors (male or female) between the ages of ≥ 18 to ≤ 45 (inclusive) will be screened as potential BM donors. Donors will be evaluated by history and physical examination. The history will include:

- History of malignancy
- Bleeding abnormalities
- Prior deep venous thrombosis
- Known cardiac or pulmonary conditions
- Prior blood transfusions
- Vaccinations
- Questions to identify persons at risks of infectious disease transmission, including Zika virus
- Questions to identify persons at risk of transmitting hematological or immunological disease
- A physician will administer the National Marrow Donor Program (NMDP) Questionnaire (a donor health history screening questionnaire).

The physical examination will include review of vital signs and evaluation for potential risks associated with the BM aspiration procedure. Prospective donors will have infectious disease testing including:

- Hepatitis B surface antigen (HBsAg)
- Anti-Hepatitis B core antibody (HBcAb)
- Anti-Hepatitis C virus antibody (HCV Ab)
- Anti-Human Immunodeficiency Virus (HIV) antibody (HIV 1/2)
- Cytomegalovirus antibody (CMV)
- HCV/HIV Nucleic Acid test
- West Nile Virus Nucleic Acid test
- Human T-lymphotropic Virus I/II (HTLV I/II)
- *T. cruzi* ELISA test (Chagas disease)

- *Zika Virus (RNA qualitative Real Time RT-PCR and/or Virus Antibody (IgM), MAC-ELISA)*
- *Rapid Plasma Reagins (RPR) or VDRL (confirmation with FTA-ABS if needed (Syphilis))*

Prospective donors will also have the following blood and urine tests:

- Complete blood count with differential
- Comprehensive metabolic panel, magnesium, calcium, and uric acid
- Urinalysis
- Serum pregnancy test (Female only)

Eligibility Criteria for Normal Donors will include:

- Male and female gender
- No history of malignancy
- No active coagulopathy and/or hypocoagulable state
- No history of cardio/pulmonary conditions
- Negative tests for Hepatitis B Surface Antigen, Hepatitis C antibody, RPR or VDRL, Chagas, HIV 1 and 2 antibody screen, HTLV I and II antibody screen, Zika Virus, and West Nile Virus.
- Hemoglobin \geq 13.0 g/dL if male; and if female donor hemoglobin \geq 11.0 g/dL
- Platelet count 140,000 to 440,000/ul
- WBC 3.0 to 11.0 K/ul
- No anomalies on the CBC and differential suggestive of a hematopoietic disorder
- Creatinine \leq 1.5 mg/dL
- ALT \leq 112 IU/L
- Bilirubin $<$ 1.5 mg/dL
- No diabetes
- Systolic blood pressure \leq 170
- Diastolic blood pressure \leq 90

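### H-Y antibody responses in women are to be judged from pre-infusion serum alone, so a treatment-induced H-Y antibody could not be seen

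*Combined protocol and SAP*

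**What the plan says.** The last sentence of Section 8.7 applies to female subjects who are given the allogeneic cells. It states that "the stored baseline serum will be analyzed to evaluate the antibody responses to HLA and H-Y antigens". It names no other sample.

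Section 8.2 places the Baseline visit within the two weeks before Day 0, and Section 8.3 adds: "The Day 0 visit will occur after all baseline tests are completed".

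A separate antibody test is planned. In Section 8.7, blood is taken from all subjects "to evaluate the presence and/or development of Panel Reactive Antibodies (PRA". Note 7 to the Time and Events Table (Section 7.1) says that PRA testing "will be performed from the serum of the subjects to check for donor specific antibodies", and sets the times: "at Baseline and Month 3 only". For blood drawn for biomarkers and PRA, Section 8.2 says that "the serum will be frozen until processed as one batch towards the end of the study".

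On donors, Section 5.1 begins "Donors (male or female) between the ages of" and goes on to the age range. Section 6.1 describes matching donor and recipient on CMV status. It does not mention sex.

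**The concern.** A sample taken before exposure cannot show a response to that exposure. The sentence stands in a section on graft rejection, is framed around women who receive the cells, and speaks of responses, yet it names only the pre-infusion sample. If it is carried out as written, the study could report an H-Y response result that contains no post-treatment information. A woman who formed H-Y antibodies after receiving cells from a male donor would be indistinguishable from one who did not. Section 10 (Statistical Analysis) does not mention antibody results, so nothing there corrects the sentence.

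**Working it through.** The plan gives no figure to reproduce. The check is one of sample timing, followed by a count of the assays needed.

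**1. Is baseline serum always pre-infusion?** Yes. The Baseline visit is 0 to 14 days before Day 0, and the infusion visit follows completion of the baseline tests. Even at 0 days the order holds.

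**2. Which antibody tests have a sample on each side of the infusion?**

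| Test | Who | Before infusion | After infusion | Source |
|---|---|---|---|---|
| PRA, for donor-specific antibodies | All subjects | Baseline | Month 3 (± 2 weeks) | Section 8.7; Table 1 and its note 7 |
| H-Y antibodies | Women only | Baseline | None named | Section 8.7, last sentence |

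PRA has one post-infusion time point and H-Y has none. With none, no change from baseline can be formed. This takes PRA in its usual sense, a screen for antibodies to HLA. The protocol does not define the panel, and nothing in it says that PRA covers H-Y. Section 8.7 introduces the H-Y analysis as an addition.

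**3. Can a woman receive male cells?** Yes, as far as the documents show. Section 5.1 admits donors of both sexes, and only CMV matching is described. The number of such pairs is not given.

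**4. Does post-infusion serum exist?** Yes. Note 7 requires serum for PRA at Month 3, and Section 8.2 has such serum frozen and run as one batch late in the study. The residual volume is not stated.

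**5. How many extra assays?** One Month 3 H-Y assay per woman treated. The planned total is 3 + 3 in the pilot phase and 5 + 5 in the randomized phase, which is 16. The number of women is not stated. If a quarter, half or all of the 16 were women, the extra assays would number 4, 8 or 16. Section 4.4 allows some withdrawn subjects to be replaced, so the ceiling is 16 plus any replacements.

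**6. Could the results be compared by dose?** Not usefully. Each dose has 3 + 5 = 8 subjects. If half were women there would be about 4 per dose, and fewer with a male donor.

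**The case against.** The strongest reply is that the sentence never says the response is to the infused cells. It is limited to women and names the baseline sample, which would fit a check for prior sensitization added to the PRA monitoring. On that reading the sample is right and only the word responses is wrong. The documents do not settle this. The setting favours a post-infusion meaning: the sentence follows directly on text about detecting T-cell activation after infusion, and the same section elsewhere separates the presence of antibodies from their development. Either way the sentence needs an edit.

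A reader might also infer that HLA responses go undetected, since the sentence names HLA too. The documents do not support that. PRA testing for donor-specific antibodies in all subjects at Baseline and Month 3 allows an HLA response to be assessed, although at one post-infusion time only.

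Nor does the gap defeat the monitoring for rejection as a whole. Section 8.7 also plans flow cytometry for T-cell activation, and H-Y is one closing sentence.

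Finally, little need be lost for good. Note 11 to Table 1 keeps samples for further laboratory studies in open-ended terms. That permits a later H-Y test but does not commit to one, so the plan as written still lacks it.

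**Conclusion.** The point holds for H-Y only. As specified, the H-Y analysis can describe pre-existing sensitization in women but cannot show a treatment-induced H-Y antibody in any of them. This rests on the visit order in Sections 8.2 and 8.3 and on the absence of any other mention of H-Y.

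Severity is minor. H-Y antibody is not among the primary or secondary endpoints (Sections 2.2.1 and 2.2.2), the safety variables (Section 9.1) or the stopping guidelines (Section 9.2.4). No dose decision depends on it. It is still more than loose wording if a response to the cells is what was meant, because it determines what the H-Y analysis can conclude.

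**What to change.** Amend the last sentence of Section 8.7 so that, in female recipients, stored Month 3 serum is tested for H-Y antibodies together with the baseline sample in the same batch. List new or rising H-Y antibodies subject by subject, with donor sex and dose, as description only and without a comparison between doses. For HLA, refer to the PRA schedule in note 7 and do not add a second HLA assay.

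If only prior sensitization was intended, replace antibody responses with pre-existing antibodies and draw no conclusion about an H-Y response to the cells.

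The first option costs one additional assay per woman treated, at most 16 plus any replacements. It needs no extra visit or blood draw provided that enough Month 3 serum remains after the PRA and biomarker assays, which the laboratory should confirm. An antibody that appeared and faded before Month 3 would still be missed. The second option costs only the edit.
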